### 3.3.2. Primary Endpoints

- 3.3.2.1. Peripheral Artery Disease Cohort
  - Primary Safety Outcome: Device-related seroma or infection through 5 years
  - Primary Performance Outcome: Secondary patency (revascularization) through 5 years
- 3.3.2.2. Aortic Aneurysm Cohort
  - Primary Safety Outcome: Survival through 5 years
  - Primary Performance Outcome: Primary patency through 5 years
- 3.3.2.3. Dialysis Access Cohort
  - Primary Safety Outcome: Device-related infection through 2 years
  - Primary Performance Outcome: Useable access circuit (reported as secondary patency) through 2 years

### 3.3.3. Secondary Endpoints

- 3.3.3.1. Peripheral Artery Disease Cohort
  - Limb Salvage through 1 year
  - Amputation-free survival through 1 year
  - Device-related Adverse Events through 1 year
  - Device-related infection requiring reoperation through 5 years
  - Primary Patency through 1 year
- 3.3.3.2. Dialysis Access Cohort
  - Primary patency through 1 year
  - Device-related adverse events through 1 year

No secondary endpoints have been identified for the Aortic Aneurysm Cohort.

### 4. Study Population

# 4.1. Description of Population

The study population will consist of three cohorts. Patients that have had treatment with Vascular Graft for PAD, aortic aneurysms, or dialysis access are eligible for consideration for enrollment in the registry.

Cohort	Treatment period	FU period after index procedure (years)	Number patients	Cap per site** (patient)
PAD	at least 5 years before site	5*		18 (25%) 36 (50%)
	initiation			18 (25%) 36 (50%)
Aortic Aneurysms	at least 5 years before site initiation	5*		16 (25%) 33 (50%)
Dialysis Access	at least 2 years before site initiation	2*		18 (25%) 36 (50%)
, 100000				18 (25%) 36 (50%)

\* Subject who died before the end of FU period will be not excluded from the registry.

Study staff will review patients' medical records to identify eligible patients for this retrospective data collection. The registry has been designed with standard eligibility criteria to enroll subjects for which the registry device has been intended to treat. Two sets of inclusion and exclusion criteria have been identified: general and cohort-specific criteria. Only patients who meet all of the inclusion criteria and none of the exclusion criteria (general and cohort-specific) will be included in the registry. A subject cannot be included in more than one cohort.

No vulnerable populations are included in this registry.

### 4.2. Inclusion Criteria

The Inclusion Criteria reflects the potential broad application of the device as evaluated by the medical judgement of the implanting physician. Inclusion Criteria will be evaluated at the time of initial identification as part of the retrospective device-use search using the patient health status at the time of the index procedure.

### 4.2.1. General Inclusion Criteria

- 1. Patient is willing and able to provide written informed consent or consent is waived, according to national and local regulations.
- 2. Patient was at least 18 years of age at the time of implant.

\*\* Site cannot enroll more than 25% of the total patients in each indication without sponsor approval. With sponsor approval, a single site may enroll a maximum of 50% of total patients.

### 4.2.2. PAD Cohort Inclusion Criteria

1. Patient was treated for peripheral arterial disease or peripheral arterial aneurysm requiring bypass treated

Vascular Graft at least 5 years before site initiation.

### 4.2.3. Aortic Aneurysm Cohort Inclusion Criteria

1. Patient underwent simultaneous or staged aortic aneurysm repair (open surgical AAA or TAAA) involving a

Vascular Graft at least 5 years before site initiation. Research device could have been used to replace or bypass either a diseased visceral branch or the aorta itself.

### 4.2.4. Dialysis Access Cohort Inclusion Criteria

### 4.3. Exclusion Criteria

### 4.3.1. General Exclusion Criteria

- 1. Patient was not available for follow up (on-site or remotely) at the clinical site, with the exception of death (e.g., patient lost to follow-up immediately after treatment, patients who live far away from the clinical site and are not available to share follow-up data performed locally).
- 2. At the time of treatment, patient had known coagulation disorders, including hypercoagulability, that were not amenable to treatment.
- 3. Patient was pregnant at the time of treatment.
- 4. Patient had known or suspected systemic infection or infection at the site of graft implantation at the time of implant.
- 5. Patient had a separate major interventional or surgical vascular procedure within 30 days prior to treatment. CVC catheter placement would be permitted.
- 6. Patient is already enrolled in this registry under a different cohort.

### 4.3.2. PAD Cohort Exclusion Criteria

At the time of treatment, the patient must not have met any of the following criteria:

- 1. Patient had percutaneous transluminal angioplasty (PTA) or stenting of the target artery at the anticipated site of the proximal or distal anastomosis within 30 days prior to the index procedure. Use of PTA or stenting during the index procedure is permitted.
- 2. Patient had a stroke or myocardial infarction (MI) within 6 weeks prior to the index procedure.
- 3. Patient has previous instance of Heparin-induced Thrombocytopenia type 2 or has known hypersensitivity to heparin.
- 4. Patient required composite bypass for index procedure (graft + significant length of autologous vessel). Autologous "cuffs" or patches are allowed.

### 4.3.3. Aortic Aneurysm Cohort Exclusion Criteria

At the time of treatment, the patient must not have met any of the following criteria:

1. Patient required emergency surgery due to aneurysm rupture.

## 4.3.4. Dialysis Access Cohort Exclusion Criteria

At the time of treatment, the patient must not have met any of the following criteria:

- 1. The patient had a previous documented and unsuccessfully treated ipsilateral central venous stenosis via imaging technique.
- 2. The patient was taking maintenance immunosuppressant medication at the time of implant such as rapamycin, mycophenolate or mycophenolic acid, prednisone (> 10 mg), cyclosporine, tacrolimus, or cyclophosphamide.
- 3. The patient has had a previous instance of Heparin-Induced Thrombocytopenia type 2 (HIT-2) or has known sensitivity to heparin.

A rationale for each inclusion / exclusion criterion is located in Appendix A.

# 5. Registry Procedures / Evaluations

No product- or procedure-related training is required, as the registry is designed to collect pseudo-anonymized clinical follow-up, procedure, demographic (including medical history), and device characteristic data from the patient's medical record.

Subjects were followed per clinical routine practices and this retrospective approach does not impact the future routine clinical treatment at the site. For this registry it is expected that the sites will follow this protocol to ensure scientifically sound evaluation of outcomes. There are no additional, known or foreseeable factors that may compromise the outcome of the registry or the interpretation of results; please refer to section 3.2.1 regarding minimization of bias.

### 5.1. Schedule of Events

Retrospective data collection only. Refer to section 5.8 for more details.

### 5.2. Informed Consent Process

For the inclusion of patients in the registry, the investigator should review all inclusion/exclusion criteria and, in the case of including patients who are alive and reachable at the site, the patient will be required to sign the Informed Consent Form (ICF) before enrolment in the registry.

As this study is retrospective and considering the nature of patient's disease, some patients may have died by the time they are included. The investigator is expected to make reasonable efforts to contact the potential patient, such as checking whether they are still alive, browsing through their clinical records, contacting available telephone numbers, or obtaining contact information from population and/or health care registers. If, after reasonable effort, the patients are found to be deceased or not reachable, the request for informed consent can be waived in accordance with national and local legislation.

If, during the course of the registry, patients who were not previously reachable come back to the clinical site for a visit, the investigator is expected to collect informed consent from those patients.

To protect patient privacy, patient-identifiable information (e.g., name, initials, complete birth date, and race) will not be collected.

The informed consent form will include emergency contact details for any concerns. The case history (i.e., source documents / subject chart) for each subject shall document that such informed consent was obtained, if this was obtained remotely or if the consent was waived. In case the consent was waived, the reason must be clearly described in the source document.

The EC approved consent form will be signed and personally dated by the subject and the person who conducted the informed consent discussion. The original signed informed consent form will be retained in the subject records. A copy of the signed informed consent document will be given to the subject for their records.

**For France only.** According to *Méthodologie de référence MR-004*, applicable for this retrospective registry, the investigator has to inform all pre-identified patients (all patients present in the pre-screening log) about this registry, and in particular their right to oppose the processing of their data for the scope of this registry. Regarding the processing of data of deceased persons, investigator has to make sure that the patient had not objected to it during his lifetime in writing. If not, the personal data concerning him will be collected for the scope of this registry. In this context, an Information and Non-opposition letter is prepared and sent to all patients present in the pre-screening log. The data collection will not begin until one month after the investigator sent out the non-opposition letter, to give time to the patient to read and, eventually oppose in writing his/her participation in this registry.

### 5.2.1. Remote Collection of the Informed Consent Form

Considering the low risk (see section 8, Risk Assessment) of this retrospective registry and the absence of registry-specific procedure for the patient, the remote collection of the informed consent will not adversely affect the rights and welfare of the patients.

In case the patient is unable to come to the hospital (e.g., COVID-19 pandemic, moved to another area, logistics, etc.), the discussion and collection of the consent may take place by a means other than a face to face (e.g., mailing consent documents to potential participants and discussing the registry and consent document via phone) per local regulations.

Specific procedures to ensure adequate documentation of prospective informed consent process, in accordance with regulation and best clinical practice, will be provided to the investigators in a separate document.

### 5.2.2. Vulnerable Populations

No patients deemed to be of a vulnerable population may be enrolled.

### 5.2.3. Emergent Cases

[figure not shown]
Not applicable due to retrospective nature of the registry.

# 5.3. Pre-Screening

Sites are expected to perform a search of patients treated with the registry devices within the hospital database following the site initiation performed by Gore. Upon site activation, the site staff will search in the hospital database patients who were treated with registry devices for each indication, representing patients meeting Inclusion #1 for each cohort. This search is based on the information already present in the patient medical record.

The research results will be recorded in the Pre-screening log and ordered based on patient's date of index procedure.

The pre-screening log produced with this research must be maintained at the site in order to document the reasons for exclusion for any patient preventing bias of the data. This list cannot be shared with Gore/other external individuals (CRO), but are only available at the site in the study binder for audit/inspection purposes.

### 5.4. Enrollment

Patient enrollment should be consecutive and beginning with patients with most recent treatment date and working towards earlier patients. The site should review batches of 15 consecutive patients at a time until site or study cap is reached. From the pre-screening log (sorted by most recent treatment date), the site should review the patients charts against inclusion and exclusion criteria, then check whether the patients are still alive and reachable in order to obtain consent. The patient is considered enrolled when informed consent is obtained or consent if waived.

Only patients enrolled in the study will be recorded in the EDC until the site reaches the max cap of enrolled patients planned for this study or until the cohort is completed.

If a patient identified in the pre-screening list will not be enrolled, only the principal reason will be recorded in the patient screening and enrollment log.

During the on-site monitoring visit, the CRA should review the Pre-screening log and Subject Screening and Enrollment log against the subjects recorded in the EDC, in order to prove the enrolment occurred sequentially, with the purpose of minimizing selection bias.

Patients cannot be enrolled in more than one cohort. Before enrolling a patient, sites should review the patient chart to confirm the patient is not eligible for more than one arm. If the patient is eligible for more than one arm (i.e. AAA & PAD), sites should enroll patients into the arm with the earliest treatment date.

### 5.5. Screening

Formal screening will not be performed due to retrospective nature of this registry. No screening procedures are performed, with exception of reviewing of the inclusion and exclusion criteria based on the information already present in the patient's medical record.

### 5.6. Screen Failure

For clarity, this registry defines screening failure as subjects from the pre-screening log who do not meet Inclusion/Exclusion criteria or declined consent.

However, if after the collection of the consent, the subjects do not meet eligibility criteria, the primary reason for screen failure will be documented and retained in registry records. The subject will be excluded from the registry and a replacement subject may be enrolled. Screening failure subject after obtaining ICF signature will be recorded in the EDC.

### 5.7. Randomization and or Blinding

No randomization or blinding is to be performed due to the confirmatory nature of the registry design.

### 5.8. Procedure

The registry procedures consist only of the collection of retrospective data from the source documents available at the site. Diagnostic imaging, treatment interventions, and follow up will be determined by physicians based on clinical practice standards.

### 5.8.1. Subject Chart Review

The chart reviews will be conducted by the investigator or a trained study coordinator at
each site. Records from all patients who underwent treatment
Vascular Grafts for PAD, aortic aneurysms, or dialysis
access will be identified for further screening according the inclusion and exclusion

Those subjects meeting all of the inclusion criteria and none of the exclusion criteria will be considered for data collection.

MD133246 Protocol Template

### 5.8.2. Data Elements

The following clinical routine data will be recorded in the registry database from the existing medical records of enrolled subjects.

- Subject information and Demographics (Age and sex)
- Medical History
- Index procedure information
- Discharge information
- Follow-up data, including (antiplatelet and anticoagulant therapy) and imaging reports (no imaging will be collected)
- Adverse events
- Device Deficiency
- Repeat Intervention
- Death or discontinuation

### 5.9. Repeat Interventions

Reinterventions may have been performed at the discretion of the investigator to treat AEs or maintain device performance. Any reinterventions performed will be documented on the CRF form. The components used as part of the reintervention, the date of the reintervention, procedural data and any AEs leading to reintervention will also be documented on the CRF form.

### 5.10. Follow Up

No on-site follow-up is required after the subject is included in the registry, as the registry consists of retrospective data collection only.

Follow-up data will be collected from the information already present in the medical chart at least to 5 years from the index procedure for the PAD and aortic aneurysm cohort and at least to 2 years for the dialysis access cohort. This data should include any adverse events, repeat interventions, and records of office, telephone, or imaging visits. No imaging will be collected for this registry.

In case the site recognized that the enrolled subject does not have data available regarding the last FU visit specified in the protocol, site should enter the next follow up data available (i.e. if a patient did not come in at year 5, but came in at year 6, year 6 data should be entered). If no follow up visit data is available, site staff should collect and document any past safety data (SAE, re-intervention, hospitalization, death, etc.) through the end of the follow up period specified for the cohort. If consent is waived, the site should contact relatives or general practitioner by phone to collect this data.

### 5.11. Subject Withdrawal from the Registry

Subjects who are alive at the time of their enrollment in the registry can withdraw from the registry without indicating any reasons at any time. No additional data will be collected and reported into the registry database after consent withdrawal. The sponsor may retain and continue to use any data collected before the withdrawal of consent, if not explicitly requested otherwise by the subject.

A replacement subject may be enrolled in rare event that a subject decides to withdraw from the registry before all follow-up visits have been recorded in the EDC.

### 5.12. Subject Lost to Follow Up

No subject lost to follow up are expected in this registry. According to General Exclusion criterion #1, subjects with no follow-up after treatment should not be included in the registry. All subjects that complete at least one follow-up after treatment will be enrolled.

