### 3.2.1. Management of potential confounding factors / bias

Bias will be controlled by strict adherence to the registry protocol. Sites will be monitored for compliance with registry protocol, including subject eligibility criteria, as allowed by EC regulations. In order to minimize selection bias, it is mandatory that the enrollment of patients will be consecutive in nature based on the date of the index procedure. Gore has put in place quality control in order to ensure that no selection bias is applied by the site during patient screening, please see section 5.4 for more details.

The registry is meant to retrospectively collect data for descriptive reporting as well as evaluate "real world" experience of clinical practice and patient outcomes during treatment and throughout follow-up extending up to 2-5 years, by cohort. Patient selection, diagnostic imaging and treatment interventions will be determined by physicians based on this protocol and clinical practice standards.

It is well known that excluding treated patients who are deceased or not reachable at the time of the inclusion due lack of informed consent can generate an important selection bias in retrospective study and is likely to seriously prevent the achievement of the research objectives. Therefore, for patients, who are deceased or not reachable at the time of the inclusion, the consent can be waived, according to national and local regulation. Refer to section 5.2 regarding the waived process.

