# 3.3. Registry Endpoint(s)

### 3.3.1. Definitions

Outcome	Definition
Primary Patency	
Aortic Aneurysm / PAD Cohort	Patency of the study graft without additional or secondary surgical or endovascular procedures to maintain or restore flow to the graft. The only exceptions that do not disqualify the graft for primary patency are procedures performed for disease beyond the graft and its two anastomoses.
Dialysis Access Cohort	Interval following intervention until the next access thrombosis or repeated intervention.
Secondary Patency	
Aortic Aneurysm / PAD Cohort	Patency of the study graft with additional or secondary surgical or endovascular procedures to restore flow to the graft after occlusion or stenosis of the graft or its anastomoses  The only exceptions that do not disqualify the graft for secondary patency are procedures performed for disease beyond the graft and its two anastomoses
Dialysis Access Cohort	Patency of the study graft from the time of access creation or placement until access abandonment
Limb Salvage	Freedom from an amputation above the level of the ankle of the index limb
Amputation Free survival	Freedom from an amputation above the level of the ankle of the index limb or all cause death
Device-related seroma or infection PAD Cohort	Clinical evidence of an infectious process in the direct vicinity of the access site or distal to the treated vascular site or seroma classified by the registry investigator as primarily related to the registry device

Device-related infection requiring reoperation PAD Cohort	Clinical evidence of an infectious process in the direct vicinity of the access site or distal to the treated vascular site classified by the registry investigator as primarily related to the registry device and required surgical intervention
Device-related infection  Dialysis Access Cohort	Clinical evidence of an infectious process in the direct vicinity of the access site classified by the study investigator as primarily related to the study device
Survival	All Cause survival
Device-related Adverse Events	Any untoward medical occurrence classified by the registry investigator as primarily related to the registry device

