#### Subject Lost to Follow Up

No subject lost to follow up are expected in this registry. According to General Exclusion criterion #1, subjects with no follow-up after treatment should not be included in the registry. All subjects that complete at least one follow-up after treatment will be enrolled.

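### Protocol 5.12 and its SAP copy restate General Exclusion 1 without the death exception, so a site applying them literally would omit deaths before a first follow-up and inflate 5-year aortic survival

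*Protocol*

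**What the plan says.** General Exclusion 1 (protocol 4.3.1) removes a patient who was not "available for follow up (on-site or remotely) at the clinical site, with the exception of death". The protocol summary and Appendix A carry the same exception. The footnote to the cohort table in section 4.1 adds: "Subject who died before the end of FU period will be not excluded from the registry".

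Section 5.12, on loss to follow-up, cites that criterion but gives it without the exception: "According to General Exclusion criterion #1, subjects with no follow-up after treatment should not be included in the registry". The next sentence reads: "All subjects that complete at least one follow-up after treatment will be enrolled". SAP section 4.0 repeats both sentences word for word under the same heading. The SAP has no eligibility section and mentions the death exception nowhere.

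Elsewhere the protocol is explicit about deceased patients. Section 3.2.1 warns that losing them for want of consent is a serious source of selection bias, and continues: "Therefore, for patients, who are deceased or not reachable at the time of the inclusion, the consent can be waived, according to national and local" rules. Section 5.2 sets out how the waiver works.

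For the aortic cohort, section 3.3.2 gives "Primary Safety Outcome: Survival through 5 years", and section 3.3.1 defines survival as "All Cause survival".

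**The concern.** Take a patient who died in hospital after the index operation, or at home before the first outpatient visit. Sections 4.1 and 4.3.1 keep this patient. Section 5.12 and the SAP, read on their own, do not. A site relying on 5.12 could log the patient as having no follow-up and move to the next name.

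That would matter because the patients left out are all failures on the aortic primary safety outcome. Enrolling only those who reached a first follow-up guarantees survival to that point, so the error can only raise the estimate. The same holds for amputation-free survival through 1 year in the PAD cohort, where death counts as an event. Neither the exact binomial interval (SAP 5.0) nor the Kaplan-Meier output (SAP 8.1) can repair it, because the omitted patients never enter the data.

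The written controls might not reveal it. Section 5.4 asks for only the principal reason when a pre-screened patient is not enrolled. The monitor's log review described there is meant to show that enrolment was sequential, and comparing exclusion reasons with recorded deaths is not mentioned.

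**Working it through.** **1. The rules side by side, for a patient who received the graft and died before any follow-up.**

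| Place | Result for this patient |
|---|---|
| Protocol 4.3.1, General Exclusion 1 (also summary and Appendix A) | Kept: death is excepted |
| Protocol 4.1, table footnote | Kept |
| Protocol 3.2.1 and 5.2 | Consent may be waived so that the deceased can be included |
| Protocol 5.12, first sentence quoted | Not included, if read without looking up the criterion |
| SAP 4.0, Subject Lost to Follow Up | Same as 5.12 |

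**2. The plan's own figure.** Protocol 10.2 and SAP 2.6 to 2.7 give 65 aortic patients, a survival rate of about 32% (text) or at least 33% (table), and a half-width below 12 points. A Clopper-Pearson 95% interval with n = 65 has a half-width of 11.88 points at 32% and 11.97 points at 33%. The smallest n with a half-width of at most 12 points is 64 at 32% and 65 at 33%. The sample size reproduces.

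**3. Effect of a literal reading.** Let S be true 5-year survival among all otherwise eligible patients, and d the share who died before a first follow-up and are left out. None of those patients survived 5 years, so the number of survivors is unchanged while the denominator shrinks by the factor 1-d:

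observed survival = S/(1-d)

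The documents give no value for d, so these are assumed values, with S = 33% and every site affected:

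| d (assumed) | S/(1-d) | Shift |
|---|---|---|
| 5% | 33/0.95 = 34.7% | +1.7 points |
| 10% | 33/0.90 = 36.7% | +3.7 points |
| 15% | 33/0.85 = 38.8% | +5.8 points |

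The largest of these is about half of the 12-point half-width. In the other direction, at d = 10% an observed 33% would correspond to a true 33 × 0.90 = 29.7%. To enrol 65 patients at d = 10%, a total of 65/0.90 = 72.2 would be reviewed and about 7 early deaths passed over.

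**4. Sensitivity.** The planning rate is written as a lower bound, and the shift grows with S: at S = 60% it is 3.2 points for d = 5% and 6.7 points for d = 10%. It shrinks if only some sites read 5.12 literally. With d = 5% and a quarter of patients at such sites, the result is 33/(1 - 0.25 × 0.05) = 33/0.9875 = 33.4%, a shift of 0.4 points.

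**5. PAD amputation-free survival.** The same formula applies, because an early death is also a failure on this outcome. The plan states no planning rate for it, so no figure is given here.

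**The case against.** The strongest reply is that 5.12 sets no rule of its own. It opens by pointing to General Exclusion 1, and anyone who looks that up finds the death exception. Sections 5.4 and 5.8.1 tell sites to screen charts against the inclusion and exclusion criteria, not against a short section on loss to follow-up. To leave out a recorded early death, a site would have to prefer a paraphrase to the criterion it cites, to the 4.1 footnote and to the purpose stated in 3.2.1. This stands, and it makes the bias conditional.

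A reader might go further and infer that the plan requires one completed follow-up for entry. The wording does not support that: the sentence "All subjects that complete at least one follow-up after treatment will be enrolled" says who will be enrolled, which is a sufficient condition and not a necessary one. Only the sentence before it can be read as excluding anyone, and that one defers to Exclusion 1.

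A reader might also infer that the SAP removes early deaths from the analysis. It does not. SAP 4.0 refers to the inclusion and exclusion criteria, and the analysis populations in SAP 5.0 are defined by indication and device, with no follow-up condition. The SAP copy is a matter of consistency.

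Finally, some control already exists: section 5.3 requires reasons for exclusion to be documented, and 5.4 has the monitor compare both logs with the database. Only the specific check on deaths is missing.

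What remains is that two passages misstate the criterion they cite, on a point that the protocol itself treats as a serious source of bias.

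**Conclusion.** The text conflict is certain: 5.12 and SAP 4.0 drop an exception that the cited criterion contains, and they contradict sections 4.1 and 4.3.1. The direction of bias is also certain wherever 5.12 is applied literally, since survival can then only read high.

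Whether any bias will occur, and how large, is not established. The size rests on two assumptions that the documents cannot settle: the share of patients who died before a first follow-up, and the share of sites that would read 5.12 literally. With d from 5% to 15% and every site affected, 33% reads as 34.7% to 38.8%; with partial uptake the shift can be a fraction of a point.

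A reader might conclude that the registry excludes early deaths by design, or that its aortic survival will be inflated. The documents do not support either conclusion, because the eligibility criteria and the stated intent keep deceased patients. This is a misquoted criterion to be reconciled. It is worth correcting because the error, if it happened, could not be repaired in analysis.

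**What to change.** In protocol 5.12 and in SAP 4.0 (Subject Lost to Follow Up), amend the sentence "According to General Exclusion criterion #1, subjects with no follow-up after treatment should not be included in the registry" by inserting, after the word 'treatment', the phrase 'with the exception of subjects who died'. Follow it with: 'Otherwise eligible subjects who received the registry device and died before a first follow-up are eligible for enrollment.' The reference to receipt of the device keeps this in line with the cohort inclusion criteria, and 'otherwise eligible' leaves the remaining exclusions in force.

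At the log review already planned in 5.4, have the monitor also confirm that no patient with a recorded death was excluded for lack of follow-up.

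The cost is a short edit in each document and one added check at a visit that already takes place. No design decision is reopened. Reported survival may be slightly less favourable than under a literal reading of 5.12.
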